4.1 Primary Endpoints and Assessment Methods

4.1.1 Safety

See Section 9.1.1 of the protocol.

4.1.2 Infectivity

There are no primary objectives for infectivity.

4.1.3 Immunogenicity

See Section 9.1.3 of the protocol.

4.1.4 Efficacy

There are no primary objectives for efficacy.

4.2 Secondary Endpoints and Assessment Methods

4.2.1 Safety

See Section 9.2.1 of the protocol.

4.2.2 Infectivity

See Section 9.2.2 of the protocol.

4.2.3 Immunogenicity

See Section 9.2.3 of the protocol.

4.2.4 Efficacy

There are no secondary objectives for efficacy.

4.3 Exploratory Endpoints and Assessment Methods

4.3.1 Safety

See Section 9.3.1 of the protocol.

4.3.2 Infectivity

There are no exploratory objectives for infectivity.

4.3.3 Immunogenicity

See Section 9.3.3 of the protocol.

4.3.4 Efficacy

See Section 9.3.4 of the protocol.

4.4 Derived Endpoints: Calculation Methods

4.4.1 Safety

4.4.1.1 Solicited Reactions

4.4.1.1.1 Daily Intensity

All daily records for solicited reactions will be derived into daily intensity according to the following classification: None, Grade 1, Grade 2, Grade 3, Grade 4, Grade 5 or Missing for solicited administration site reactions; and None, Grade 1, Grade 2, Grade 3, or Missing for solicited systemic reactions.

For non-measurable solicited reactions, daily intensities will correspond to daily records reported in the clinical database and grade reported as “unknown” will be considered as “Missing”. When in the CRF presence is recorded as “No” and with all daily records missing then all daily intensities will be derived as “None”

For measurable solicited reactions the daily measurements reported in the clinical database will be converted based upon the intensity scales defined in the Section 9.1.1.3.2 of the protocol. Note the intensity could be considered “None” (not a reaction) in the analysis despite being considered a reaction by the investigator.

Note: The maximum intensity on the ongoing period is derived from the record of the maximum intensity/measurement after the end of the solicited period following the rule described above.

4.4.1.1.2 Maximum Overall Intensity

Maximum overall intensity is derived from the daily intensities computed as described in Section 4.4.1.1.1 and is calculated as the maximum of the daily intensities over the period considered.

4.4.1.1.3 Presence

Presence is derived from the maximum overall intensity on the period considered:

- None: No presence

- Grade 1, Grade 2, Grade 3, Grade 4, Grade 5: Presence
- Missing or Unknown: Missing presence

Participants with at least one non-missing presence for a specific endpoint will be included in the analysis. Conversely, those without a non-missing presence will not be included in the analysis of the endpoint.

The time period is displayed as D0-D3, D4-D7, D8-D14, D15-D28, D29 or later.

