9.1.1.2 Safety Endpoints

The primary endpoints for the evaluation of safety are as follows (in all infants and toddlers regardless of baseline serostatus):

- Occurrence of any unsolicited systemic AEs reported in the 30 minutes after each and any vaccination.
- Occurrence of solicited (i.e., pre-listed in the participant's DC / eDC and in the CRB) administration site and systemic reactions within 28 days after each and any vaccination (i.e., Acute Phase).
- Occurrence of any unsolicited (spontaneously reported) AEs within 28 days after each and any vaccination (i.e., Acute Phase).
- Occurrence of any AESIs within 28 days after each and any vaccination.
- Occurrence of any MAAEs within 28 days after each and any vaccination.
- Occurrence of any SAEs throughout the study period.
- Other safety endpoints will be recorded or derived as described in the statistical analysis plan. Depending on the item, these could include nature (Medical Dictionary for Regulatory Activity [MedDRA] preferred term), time of onset, duration, number of days of occurrence, intensity, relationship to vaccine, action taken, whether the AE led to early termination from the study, seriousness, or outcome.

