9.1.1.3.2 Reactogenicity (Solicited Reactions from Day 0 to Day 28 After Each Vaccination)

After each vaccination, the participant's parents / guardians / legally authorized representatives will be provided with a DC / eDC, and a digital thermometer, and will be instructed how to use them. The following items will be recorded by the participants in the diary card / electronic diary card on the day of vaccination and for the next 28 days (i.e., Day 0 through Day 28) until resolution:

- Daily temperature, with the route by which it was taken
- Daily measurement and intensity grade of any solicited administration site reactions (e.g., runny nose) and systemic reactions (e.g., fever)
- Action taken for each event (e.g., medication)

The action(s) taken by the parent / guardian / legally authorized representative to treat and/or manage any solicited reactions will be classified in the CRB using the following list (all applicable items should be checked):

- None
- Medication
- Health care provider contact
- Hospitalized
- Discontinuation of study vaccination

Parents / guardians / legally authorized representatives of study participants will be contacted by telephone each day for the first 7 days after each vaccination and then 3 times weekly after the D07 visit to remind them to record all safety information in the diary card / electronic diary card.

If the timing of the telephone call should fall on a weekend or a holiday, the call should be made on the next business day. If contact is not made on the designated day, study staff will continue calling until contact is made. Every telephone attempt and its outcome will be documented in the source document.

[Table 9-1](#) and [Table 9-2](#) present, respectively, the administration site reaction that is pre-listed in the diary cards and CRB, together with the intensity scales.

Table 9-1: Solicited administration site reactions: terminology, definitions, and intensity scales

CRB term (MedDRA lowest level term [LLT])	Rhinorrhea	Nasal congestion
Diary card term	Runny nose	Stuffy or blocked nose
Definition	
Two or more consecutive days of clear, mucous or purulent discharge from the nose.
 
Note: Not associated with crying, change of room temperature, or eating and drinking.
	
Two or more consecutive days of stuffy or blocked nose.
 
Note: Not associated with crying, change of room temperature, or eating or drinking.

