Intensity scale*	
Grade 1 (mild): No medical intervention required; may include use of over-the-counter medications managed by the caregiver for treatment of symptoms
 
Grade 2 (moderate): Outpatient medical intervention by a health care provider required; may include use of over-the-counter and/or prescription medications
 
Grade 3 (severe): Prolonged medical intervention and/or hospitalization required
 
Grade 4 (life-threatening): Illness requiring hospitalization with intensive care
 
Grade 5 (death): Event resulting in fatal outcome to the participant
	
Grade 1 (mild): No medical intervention required; may include use of over-the-counter medications managed by the caregiver for treatment of symptoms
 
Grade 2 (moderate): Outpatient medical intervention by a health care provider required; may include use of over-the-counter and/or prescription medications
 
Grade 3 (severe): Prolonged medical intervention and/or hospitalization required
 
Grade 4 (life-threatening): Illness requiring hospitalization with intensive care
 
Grade 5 (death): Event resulting in fatal outcome to the participant

* For the measurable reactions of rhinorrhea and nasal congestion, the parent / guardian / legally authorized representative will decide whether or not medical intervention was required and if so the type of intervention, and the classification as Grade 1 - 5 will be assigned at the time of review of the diary card.

Table 9-2: Solicited systemic reactions: terminology, definitions, and intensity scales

CRB term (MedDRA lowest level term [LLT])	Fever	Vomiting	Crying abnormal	Drowsiness	Appetite lost	Irritability
Diary card term	Temperature	Vomiting	Abnormal crying	Drowsiness	Loss of appetite	Irritability
Definition	Elevation of temperature to $\geq 38.0^{\circ}\text{C}$ ($\geq 100.4^{\circ}\text{F}$)	Vomiting does not include spitting up	Inconsolable crying without a determined reason	Reduced interest in surroundings, or increased sleeping	See intensity scale	An excessive response to stimuli: increased fussiness, whining, and fretfulness despite attempts to comfort the infant and despite caregiver responses that would normally be soothing

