4.4.1.1.5 Number of Days of Presence During the Solicited Period

Number of days of presence over the period considered is derived from the daily intensities computed as described in Section 4.4.1.1.1. It corresponds to the number of days with daily intensities of Grade ≥ 1 . Number of days of presence on the solicited period with a specified intensity may also be derived.

Number of days of presence during the solicited period is displayed as 1-3 days, 4-7 days, 8-14 days, 15-28 days, 29 days.

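### The SAP derives presence, onset and days of presence of runny and blocked nose from any single Grade 1 day, without the protocol's condition of two consecutive days

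*SAP*

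**What the plan says.** Protocol 9.1.1.3.2, Table 9-1, has a definition row and a separate intensity scale for each nasal reaction. Rhinorrhea is defined as "Two or more consecutive days of clear, mucous or purulent discharge from the nose" and nasal congestion as "Two or more consecutive days of stuffy or blocked nose". The intensity scale grades by the medical intervention needed; Grade 1 means that none was needed. The diary captures "Daily measurement and intensity grade of any solicited administration site reactions", and the table footnote says of the nasal terms that the "classification as Grade 1 - 5 will be assigned at the time of review of the diary card". Occurrence of solicited administration site reactions within 28 days of each vaccination is a primary safety endpoint (Protocol 9.1.1.2).

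The SAP builds its variables in a chain:

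- Daily intensity comes from the intensity scales of Protocol 9.1.1.3.2 (4.4.1.1.1).
- Overall intensity is the maximum of the daily values (4.4.1.1.2).
- Presence follows from that maximum: "Grade 1, Grade 2, Grade 3, Grade 4, Grade 5: Presence" (4.4.1.1.3).
- Onset is the first day of Grade 1 or more (4.4.1.1.4).
- Days of presence counts every such day: "Number of days of presence during the solicited period is displayed as 1-3 days" is the lowest class (4.4.1.1.5).

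For the safety endpoints themselves, SAP 4.1.1 says only "See Section 9.1.1 of the protocol".

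**The concern.** The SAP takes the grading scale from the protocol table and leaves the definition behind. For fever this does no harm, because Grade 1 starts at 38.0°C, which is also the threshold in the definition. The nasal scale has no such floor: a single day of mild runny nose with no intervention meets Grade 1 and does not meet the definition. A scale-only derivation therefore loses the two-day condition for exactly these two terms.

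They are the whole of the solicited administration site category, and they are the local reactions that matter most for a live intranasal vaccine. If one-day symptoms are common in infants over a 29-day diary, the reported rates would answer a different question from the one the protocol set. The contrast with placebo, which is there to show background illness, could be blurred.

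**Working it through.** **Step 1. Apply both rules to the same 29-day record (D0 to D28).** SAP rule: present if the maximum daily grade is at least 1. Protocol rule: present if two consecutive days have Grade 1 or more.

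| Diary record | SAP: present, days | Protocol definition |
|---|---|---|
| One Grade 1 day | yes, 1 | not met |
| Isolated days D3, D9, D20 | yes, 3 | not met |
| Two consecutive days | yes, 2 | met |
| All 29 days | yes, 29 | met |

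The SAP rule gives a minimum of 1 day and a maximum of 29, which matches the lowest and highest classes in SAP 4.4.1.1.5. Every record that meets the protocol definition also meets the SAP rule, but not the reverse. On the same database, the SAP rate is therefore equal to or higher than the protocol-defined rate.

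**Step 2. Onset.** With an isolated day on D3 and a two-day run on D9 and D10, the SAP dates onset at D3. The protocol-defined reaction starts on D9.

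**Step 3. Is a two-day rule hidden elsewhere?** SAP 4.4.1.1.6 shows overall days of presence from a lowest class of 2 to 3 days. This comes from its formula for reactions still ongoing after the period. With one day in the period and an end date on D29, it gives 29 + 1 − 29 + 1 = 2. It is not a two-day condition.

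**Step 4. Possible size.** The documents give neither expected nasal rates nor the frequency of isolated days, so all inputs here are assumptions. Let p be the protocol-defined rate, q the daily risk of an isolated day and f the chance of at least one over 29 days:

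- f = 1 − (1 − q)^29
- SAP rate = 1 − (1 − p)(1 − f) = p + (1 − p)f
- With the same q in both arms, difference = (p_vaccine − p_placebo)(1 − f)

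With p = 45% (vaccine) and 30% (placebo):

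| q per day | f | SAP rate, vaccine | SAP rate, placebo | Difference |
|---|---|---|---|---|
| 0 | 0% | 45% | 30% | 15.0 points |
| 0.5% | 14% | 52% | 39% | 13.0 |
| 1% | 25% | 59% | 48% | 11.2 |
| 2% | 44% | 69% | 61% | 8.3 |

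The first row is the case in which no graded single day reaches the database.

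**Step 5. Dependence on equal risk.** If q were 1% in the vaccine arm and 0.5% in the placebo arm, the difference would be 58.9% − 39.5% = 19.4 points, wider than the true 15. Shrinkage is therefore conditional. The upward direction of each arm's rate is not.

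**The case against.** The strongest reply is that the two-day condition may be applied before the SAP derivation begins. Nasal grades are assigned when the diary card is reviewed, and a reviewer looking back can see whether days are consecutive. Protocol 9.1.1.1 treats an event that misses the pre-listed conditions as an unsolicited AE, and SAP 4.1.1 refers back to the protocol section that contains Table 9-1. If sites screen in this way, the SAP rule changes nothing.

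This stands as a possibility. A reader might infer that the rates are certainly inflated in every arm, and the documents do not support that. Nor do they say that screening takes place. The Table 9-1 footnote ties the grade to the intervention required, not to duration. The diary is graded daily and reviewed by daily telephone calls in the first week, when a second day may not yet have happened. The footnote calls these reactions measurable, and for measurable reactions the SAP lets its own conversion overrule the investigator's view. If screening is left to about 40 sites without a written rule, practice may differ between them.

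Three further objections hold. A reader might take the class of 1 to 3 days as proof that single nasal days are counted, but that class serves all solicited reactions, including those for which one day is enough. Isolated days may be vaccine-related, so dilution cannot be assumed. A bare two-day rule could also undercount: it would drop an episode that starts on D28 and continues, and one split by a missed diary entry.

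Finally, the analyses are descriptive, and over-counting mild reactions is cautious for an absolute rate. That limits the consequence but does not remove the mismatch with the protocol definition.

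**Conclusion.** The point holds as a conflict between the SAP's written derivation and the protocol's definition of a primary safety endpoint. Unless single days are removed at diary review, nasal reaction rates can exceed the protocol-defined rates in any arm and cannot fall below them, and onset can be too early. If isolated-day risk is similar across arms, the difference from placebo shrinks.

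The amount is unknown and may be zero. The fall from 15 to about 8 points is an illustration that rests on assumed rates of 45% and 30% and an equal isolated-day risk of up to 2% per day. The documents do not support a statement that the rates are inflated, or by how much. The correction should be made because it is cheap and settles what the endpoint means.

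**What to change.** In SAP 4.4.1.1.3 to 4.4.1.1.5, add a rule for rhinorrhea and nasal congestion only:

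- Presence requires Grade 1 or more on at least two consecutive days.
- Onset is the first day of the first such run.
- Days of presence counts days within such runs.
- An onset on D28 that is ongoing after D28 (as derived in SAP 4.4.1.1.7) meets the condition.
- One missing diary day between two days of Grade 1 or more does not break a run. This needs an explicit exception, because SAP 4.4.1.1.4 treats a missing day as a gap.

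Present the any-single-day count as a supportive row, so that no safety information is lost. State in the SAP and the CRF completion instructions whether sites are to record single nasal days, so that both counts can be interpreted.

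If the sponsor prefers the any-day rule as the main count, list it in SAP 5.7 as a departure from Table 9-1 and show the protocol-defined count beside it.

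The cost is a few sentences of SAP text, a clarification in the CRF instructions and one derivation on daily data that the protocol already collects. If sites have already screened out single days, the any-day row cannot be recovered from the database and the report should say so.

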4.4.1.1.4 Time of Onset

Time of onset is derived from the daily intensities computed as described in Section 4.4.1.1.1. It corresponds to the first day with intensity of Grade ≥ 1 .

Note: If a reaction is not continuous (i.e., reaction occurs over two separate periods of time intervened by at least one daily intensity Missing or None) then the time of onset is the first day of the first occurrence.

Time of onset period is displayed as D0-D3, D4-D7, D8-D14, D15-D28.

4.4.1.1.5 Number of Days of Presence During the Solicited Period

Number of days of presence over the period considered is derived from the daily intensities computed as described in Section 4.4.1.1.1. It corresponds to the number of days with daily intensities of Grade ≥ 1 . Number of days of presence on the solicited period with a specified intensity may also be derived.

Number of days of presence during the solicited period is displayed as 1-3 days, 4-7 days, 8-14 days, 15-28 days, 29 days.

4.4.1.1.6 Overall Number of Days of Presence

If a reaction is ongoing at the end of the solicited period, then the overall number of days of presence is derived from the daily intensities and the end date of the reaction after the end of the solicited period. The overall number of days of presence is:

- $(\text{end date} - \text{last vaccination date}) + (\text{number of days of presence within the solicited period}) - \text{length of the solicited period} + 1$

If the end date is missing or incomplete (contains missing data [MD]), the overall number of days of presence will be considered as Missing.

Overall number of days of presence is displayed as 2-3 days, 4-7 days, 8-14 days, 15-28 days, 29 days or more, and Missing end date.

4.4.1.1.7 Ongoing

Ongoing is derived from the last daily intensity of the solicited period computed as described in Section 4.4.1.1.1 and the maximum intensity on the ongoing period. The investigator's ongoing flag is not used because the measurement would determine the ongoing status of the reaction.

Note the intensity could be considered None (not a reaction) in the analysis despite being considered a reaction by the investigator.

- Ongoing: if the last daily intensity of the solicited period is at least Grade 1 and the maximum intensity on the ongoing period is at least Grade 1
- Not ongoing: if the last daily intensity of the solicited period is None or the maximum intensity on the ongoing period is None.
- Missing: all other conditions (in this case, it is not included in the denominator of the ongoing analysis in the safety tables).

4.4.1.2 Unsolicited AEs

4.4.1.2.1 Presence

An observation will be considered an event if it has at least a verbatim term and is not a Grade 0 intensity event.

Grade 0 events are not included in safety analysis but are included in separate listings.

4.4.1.2.2 Intensity

Intensity will be derived according to the following classification: None, Grade 1, Grade 2, Grade 3, or Missing. For AESI (except wheezing), intensity will be graded using the following classification: None, Grade 1, Grade 2, Grade 3, Grade 4, Grade 5 or Missing as defined in Section 9.1.1.3.5 of the protocol.

If the unsolicited AE is measurable and its preferred term is part of the list of solicited reactions, then the measurement is derived based upon and following the same rule than the intensity scales defined in Section 9.1.1.3.2 of the protocol for that measurable solicited reaction. Note the intensity could be considered “None” (not a reaction) in the analysis despite being considered a reaction by the investigator.

Intensity for the other unsolicited AEs will correspond to the value reported in the eCRF.

The maximum intensity corresponds to the highest intensity for a unique term.

4.4.1.2.3 Last Vaccination

Last vaccination before an unsolicited AE is derived from the start date of the unsolicited AE provided in the eCRF and is calculated as follows:

- If an unsolicited AE has a complete start date and different to any of the vaccination dates, the start date is used to determine the last vaccination before the unsolicited AE
- If the start date is missing or partially missing, or equal to any vaccination date, then the visit number in the “Appeared after Visit” or similar field, is used to determine the last vaccination before the unsolicited AE.

4.4.1.2.4 Time of Onset

Time of onset is derived from the start date of the unsolicited AE and the date of last vaccination as described in Section 4.4.1.2.3:

- start date of the unsolicited AE – date of last vaccination before the unsolicited AE

The time of onset is considered as missing only if one or both dates are missing or partially missing.

The unsolicited AEs will be analyzed “within 28 days” after each vaccination (i.e. acute phase), which corresponds to AEs with a time of onset between 0 and 28 days. An AE with missing time of onset will be considered to have occurred just after the last vaccination (computed according to the Section 4.4.1.2.3), so will be included in these tables.

Time of onset period is displayed as D0-D3, D4-D7, D8-D14, D15 or later, and Missing.

Note: Unsolicited AE that occurred before vaccination (negative time of onset) or with a time of onset higher than defined above will not be included in analysis but will be listed separately.

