11.1 Data Collection and CRB Completion

Individual diary cards / electronic diary cards, specifically designed for this study by the Sponsor and provided to the study sites, will be given to study participants for the recording of daily safety information as described in [Section 9.1.1.3](#). These diary cards / electronic diary cards will include pre-listed terms and intensity scales (see [Table 9-1](#) and [Table 9-2](#)) as well as areas for free text to capture additional safety information or other relevant details. Parents / guardians / legally authorized representatives will also be provided with standard digital thermometers for measuring daily temperatures. To ensure consistency of reporting, the study sites will instruct parents / guardians / legally authorized representatives on how to correctly use these tools.

During the period between the final vaccination and the final visit, follow-up will be done by interviewing participants either during a visit or over the telephone using a questionnaire to capture SAEs, MAAEs and AESIs, if applicable. A memory aid may be provided to the participants at the preceding study visit to help them record information on events occurring between this visit and the 6-month follow-up.

Relevant information will be transcribed into the AE CRF. Any SAEs captured during this 6-month follow-up period will be reported and followed-up as per the normal process for reporting SAEs.

At specified intervals, the Investigator or an authorized designee will interview the parents / guardians / legally authorized representatives to collect the information recorded in the diary card / electronic diary card and will attempt to clarify anything that is incomplete or unclear. All clinical study information gathered by the study site will be reported electronically by the Investigator or authorized designee using a web-based CRB. (Any information that was not documented in the diary card / electronic diary card will first be captured in the source document and then reported electronically.) The CRB has been designed specifically for this study under the responsibility of the Sponsor, using a validated Electronic Records / Electronic Signature-compliant platform (21 CFR Part 11).

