4.4.1.2.8 Serious Adverse Events

An event will be considered as a serious event if “Yes” is checked for “Serious” in the eCRF.

SAEs will be analyzed throughout the study using the following periods:

- Within 28 days after vaccination
- During the study (i.e., all SAEs occurred during the study)

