5.3.1.4 Start Date and End Date

Missing or partially missing start dates or end dates for unsolicited AEs (including SAEs) will remain missing and not be imputed. If the start date is missing or partially missing, the time of onset will be considered to be missing. Nevertheless, unsolicited AEs with missing time of onset will be included in analyses according to the last vaccination (computed according to the Section 4.4.1.2.3). If either the start date or end date is missing or partially missing, the duration will be considered missing.

Missing or partially missing end dates for ongoing solicited AEs will remain missing and not be imputed.

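### An SAE whose recorded month or visit proves late onset is still tabulated within 28 days of the last vaccination if the day of onset is missing

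*SAP*

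**What the plan says.** SAP 4.4.1.2.4 computes time of onset for an unsolicited AE as its start date minus the date of the last vaccination. "The time of onset is considered as missing only if one or both dates are missing or partially missing", so a record with month and year but no day is handled like a blank date. The section continues: "An AE with missing time of onset will be considered to have occurred just after the last vaccination", and "so will be included in these tables", meaning the tables restricted to "AEs with a time of onset between 0 and 28 days".

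SAP 5.3.1.4 leaves missing and partial dates unimputed, names SAEs explicitly, and repeats that "unsolicited AEs with missing time of onset will be included in analyses according to the last vaccination".

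SAP 4.4.1.2.3 decides which vaccination was the last one. Its second bullet begins "If the start date is missing or partially missing, or equal to any vaccination date, then the visit number in the" and goes on to name the Appeared after Visit field. That field has no other stated use.

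SAP 4.4.1.2.8 tabulates SAEs over two periods: "Within 28 days after vaccination", and the whole study. Protocol 9.1.1.3.3 collects SAEs from enrollment to the last visit, but asks parents to record other medical events only for 28 days after each vaccination. Protocol 11.1 adds interviews between the final vaccination and the final visit, "using a questionnaire to capture SAEs, MAAEs and AESIs, if applicable".

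**The concern.** A conservative default makes sense when nothing is known about timing. This rule goes further. It also applies when the record itself shows that onset was outside the window, because the known month and year are discarded and the visit field only selects a dose.

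SAEs are where this can go wrong. They are collected for up to 12 months, most of which lies outside any 28-day window. They count as unsolicited AEs (protocol 9.1.1.1), and unsolicited AEs within 28 days of vaccination are a primary safety endpoint (protocol 9.1.1.2). A late SAE without a recorded day would therefore be reported as an acute post-vaccination event, both in the SAP's 28-day SAE period and in the primary 28-day unsolicited AE table.

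The rule applies equally to vaccine and placebo groups, so it is not reliably conservative for a comparison. A misplaced event can create a difference or dilute one.

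**Working it through.** **The plan's own figures.** The plan gives no figure for partly dated events. Its only planning figures for safety counts are the detection probabilities in protocol 12.5 and SAP 5.5, and both reproduce:
- Low dose: 1 − 0.97^100 = 95.2%, stated as 95%.
- High dose: 1 − 0.9625^80 = 95.3%, stated as 95%.

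The point does not depend on them, but they fix the denominators of 100 and 80 used below.

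**Scoring one record literally.** Take a Cohort 3 child vaccinated on 10 May 2021, within the enrollment period in protocol 5.1.5, with an SAE dated January 2022, day unknown.
1. The start date is partly missing, so onset is missing (SAP 4.4.1.2.4).
2. Cohort 3 has one vaccination, so the last vaccination is 10 May 2021 (SAP 4.4.1.2.3).
3. The event is treated as just after that vaccination and enters the 28-day tables (SAP 4.4.1.2.4 and 5.3.1.4).
4. The earliest possible onset is 1 January 2022, day 236. The latest is 31 January 2022, day 266.
5. The note in 4.4.1.2.4 that removes late events cannot act, because it needs a computed onset.

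The result contradicts the month on the record.

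**How often the month alone settles it.** For a given last vaccination date, each calendar month to the end of follow-up is surely inside, possibly inside or surely outside days 0 to 28. The dates are the planned ones in protocol 5.1.5. The Cohort 4 row assumes exactly the minimum 5 months of follow-up.

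| Last vaccination | End of follow-up | Inside | Possible | Outside |
|---|---|---|---|---|
| Cohort 1, 3 Sep 2020 | 30 Apr 2021 | 1 | 1 | 6 |
| Cohort 1, 27 Oct 2020 | 30 Apr 2021 | 1 | 1 | 5 |
| Cohort 2 dose 2, 5 Feb 2021 | 31 Oct 2021 | 1 | 1 | 7 |
| Cohort 2 dose 2, 26 Apr 2021 | 31 Oct 2021 | 1 | 1 | 5 |
| Cohort 3, 31 May 2021 | 30 Apr 2022 | 1 | 1 | 10 |
| Cohort 4 dose 2, 27 Jul 2021 | 27 Dec 2021 | 1 | 1 | 4 |

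The SAP rule places every month in every row within 28 days. A rule that used the recorded month would place at most two per row there.

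**Effect of one misplaced event.** These are Clopper-Pearson limits, the SAP's method. For zero events the upper limit is 1 − 0.025^(1/n); for example, 1 − 0.025^(1/80) = 4.5%. For one event it is the 97.5th percentile of Beta(2, n − 1).

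| n | Group | Upper limit, 0 events | Estimate and upper limit, 1 event |
|---|---|---|---|
| 100 | Low dose, pooled | 3.6% | 1.0%, 5.4% |
| 80 | High dose, pooled | 4.5% | 1.25%, 6.8% |
| 120 | Placebo, pooled | 3.0% | 0.83%, 4.6% |
| 20 | One arm of Cohort 1, 2 or 3 | 16.8% | 5.0%, 24.9% |

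The last row matters because SAP 5.1 also analyzes by cohort.

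**The case against.** The strongest reply is that the rule is a deliberate, visible worst-case convention that will seldom be used. It matches the plan's other defaults: a missing relationship counts as related, and the worst case is taken after any vaccination. In the onset display the event appears under Missing, not in the first days, and listings flag missing dates. SAEs are also the events least likely to lack a day. Families are asked to notify the site immediately, SAEs are reported within 24 hours (protocol 10.1), and data are queried and reconciled (protocol 11.2). All of this stands, and it keeps the point small. It does not justify overriding a month that is on the record.

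A reader might infer more than the documents support:
- **That all unsolicited AEs are affected.** Non-serious AEs are recorded only for 28 days after each vaccination, and MAAE and AESI collection is specified for the same 28 days (protocol 9.1.1.3.4 and 9.1.1.3.5). Later MAAEs or AESIs could arise only through the qualified wording in protocol 11.1 or through illness visits.
- **That the primary SAE endpoint is distorted.** That endpoint covers the whole study and does not change. The 28-day SAE period is a SAP sub-period.
- **That memory-aid recall will produce many undated events.** The reporting duties above point the other way.
- **That any event appearing after Visit 05 is outside the window.** Visit 05 may fall on day 28 after dose 2, and day 28 counts as inside. The actual visit date is needed.

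**Conclusion.** The point holds in a narrow form. The rule as written assigns an event to the 28-day tables even when its recorded month and year, or the visit after which it appeared, rule that out. In practice it concerns SAEs, plus any MAAE or AESI recorded after day 28. After a first dose in the two-dose cohorts, the misplacement is about two months at most; after the last dose it can be many months.

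The counts at risk are the 28-day SAE period and the primary 28-day unsolicited AE table, with the MAAE and AESI tables exposed only if late events are so flagged. The number of affected events is not given and may be zero, so the changes in the limits illustrate a single event and do not forecast one. The calendar check rests on the planned dates in protocol 5.1.5. It is a small correction worth making before the tables are programmed, and no reason to doubt the safety analysis as a whole.

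**What to change.** In SAP 4.4.1.2.4 and 5.3.1.4, keep inclusion within 28 days of the last vaccination as the default for a missing or partial start date, with one exception: the event is excluded when its earliest possible onset is more than 28 days after that vaccination. Define earliest possible onset as the later of (a) the first day of the known month, or of the known year if the month is missing, and (b) the actual date of the visit named in the Appeared after Visit field. Excluded SAEs stay in the whole-study SAE table, and all excluded events stay in the listings.

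The cost is one sentence in the SAP and a short programming check on fields already collected. Dates that cannot be resolved remain in the 28-day tables.
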